**Table 2: Dosage and Administration Table for Study Interventions and Combination Drugs**

Group	Group A	Group B		Group A and Group B	
Intervention Name	BDQ (TMC207) a,b	Rifamycin a,b,c		clarithromycin (CAM)	ethambutol (EB)
		rifampicin (RFP)	rifabutin (RBT)		
Category	Study Interventions (Investigational Medicinal Product)			Non-Investigational Medicinal Product	
	Study drug	Comparator		Combination drugs	
Formulation and strengths	100 mg tablet	150 mg capsule	150 mg capsule	200 or 250 mg tablet	125, 250, 400 or 800 mg tablet
Dosage level(s)	JP, SK, TW: Loading phase (Week 1-2): 400 mg qd, Maintenance phase (Week 3-48): 200 mg biw with at least 72 hours between doses	JP, SK, TW: 450 mg qd, Maximum daily dose 600 mg	JP: 300 mg qd SK, TW: 150 or 300 mg qd	JP: 800 mg/day d (400 mg bid) SK, TW: 1,000 mg/day d (500 mg bid)	JP: 500-750 mg qd, Maximum daily dose 1.0 g SK, TW: 15 mg/kg e qd
Route of administration	Oral	Oral	Oral	Oral	Oral
Sourcing	Provided centrally by the sponsor			Provided locally by the trial site	
a Participants who are taking rifamycin before start of treatment with BDQ will be required to discontinue rifamycin to allow for a minimum 14-day washout period to avoid DDIs between rifamycin and BDQ. b Bedaquiline and rifamycin (RFP/RBT) will be provided under the responsibility of the sponsor. c RFP is basically administered in all countries, but RBT will be considered if RFP is ineffective or cannot be used in Japan or at the discretion of the investigator in South Korea and Taiwan. The dose of RBT is based on the recommended dose in each country; 300 mg/day in Japan, and 300 mg/day for ≥50 kg and 150 mg/day for <50 kg in South Korea and Taiwan. d Daily dose of CAM on Day 1 is 800 mg (400 mg bid) in Japan and 1,000 mg (500 mg bid) in South Korea and Taiwan. If a dose reduction is required due to AEs after the start of treatment, the daily dose of CAM may be reduced to 750 mg (South Korea and Taiwan) or 600 mg (Japan) at the discretion of the investigator. e Based on 15 mg/kg, the daily dose will be determined at the discretion of the investigator.					
Key: JP=Japan; SK=South Korea; TW=Taiwan; AE=adverse event; BDQ=bedaquiline; bid: bis in die (twice a day), biw: bis in week (twice a week); qd: quaque die (once a day), CAM=clarithromycin; EB=ethambutol; RBT=rifabutin; RFP=rifampicin; DDI= drug-drug interactions					

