**Pharmacokinetic Analyses**

If feasible, population PK analysis of plasma BDQ (and M2 [optional]) concentration-time data of BDQ (and M2 [optional]) may be performed using nonlinear mixed-effects modeling. Data may be combined with those of other selected studies to support a relevant structural model. Available baseline participant characteristics (demographics, laboratory variables, genotypes, race, etc) will be tested as potential covariates affecting PK parameters. Details will be given in a population PK analysis plan and the results of the population PK analysis will be presented in a separate report.

A snapshot date for PK samples to be analyzed will be defined, if required. Samples collected before this date will be analyzed for BDQ (and M2 [optional]) and included in the population PK analysis. Samples collected after the snapshot date will be analyzed at a later date and may be included in a population PK re-analysis when they become available after database lock.

Data will be listed for all participants with available plasma concentrations per intervention group.

For each intervention group, descriptive statistics, including arithmetic mean, SD, coefficient of variation, median, minimum, and maximum will be calculated for all individual derived PK parameters including exposure information of BDQ and M2 (if applicable) for Group A, and will be calculated for predose and 2 to 4 hours postdose plasma concentrations on Day 1, Weeks 2, 8, 12, 24, and 48 (for Week 48, BDQ and M2 only) of BDQ, and CAM and 4-OH CAM for both Groups A and B.

All plasma concentrations below the lowest quantifiable concentration or missing data will be labeled as such in the concentration data presentations or SAS dataset. Concentrations below the lower quantifiable concentration will be treated as zero in the summary statistics. All participants and samples excluded from the analysis will be clearly documented in the Clinical Study Report.

Mean and median plasma BDQ, M2, CAM and 4-OH CAM concentration time profiles will be plotted after the first dose of BDQ, and individual serum concentration time profiles may also be plotted.

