
 
Clinical assessment: To evaluate the efficacy of BDQ compared with rifamycin when administered as part of a treatment regimen with CAM and EB in adult participants with treatment-refractory MAC-LD.
 
	
 
Change from baseline in patient-reported health status on total score of SGRQ at Weeks 48 and 60.
 
Change from baseline in lung function parameters at Weeks 24, 48, and 60.
 
Percentage of participants who undergo a change in their MAC-LD treatment regimen by Week 24, by Week 48 (Group A) and by Week 60 (Group B).
 

 
Microbiological assessment: To evaluate the efficacy of BDQ compared with rifamycin when administered as part of a treatment regimen with CAM and EB in adult participants with treatment-refractory MAC-LD at Week 60.
 
	
 
Percentage of participants with sputum culture conversion (defined as 3 consecutive negative sputum cultures taken at least 25 days apart) in MGIT and 7H10 or 7H11 agar media at Week 60.
 

 
To evaluate the safety and tolerability of BDQ compared with rifamycin when administered as part of a treatment regimen with CAM and EB in adult participants with treatment-refractory MAC-LD.
 
	
 
Safety and tolerability based on assessment of AEs, clinical laboratory assessments, 12-lead ECG, vital signs, physical examination, visual examination, and audiology up to Week 60.
 

 
To evaluate the PK of BDQ (and metabolite M2), and CAM (and metabolite 14-OH-CAM [optional]).
 
	
 
PK exposures of BDQ (and metabolite M2 [optional]) at Day 1, Weeks 2, 8, 12, 24, and 48, and CAM (and metabolite 14-OH-CAM [optional]) at Day 1, Weeks 2, 8, 12, and 24.
 

Exploratory	

 
Clinical assessment: To evaluate the efficacy of BDQ compared with rifamycin when administered as part of a treatment regimen with CAM and EB in adult participants with treatment refractory MAC - LD assessed by QOL-B NTM module.
 
	
 
Change from baseline in patient reported health status on score of QOL-B NTM module at Weeks 24, 48, and 60.
 

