##### **5.7.1.1. Statistical Analysis of Pharmacokinetics: (Descriptive Statistics)**

Descriptive statistics (N, mean, standard deviation, %CV, median, minimum and maximum) will be calculated to summarize plasma BDQ, M2, CAM and 14-OH-CAM concentrations at each sampling time point by intervention group and study day (Day 1, Weeks 2, 8, 12, 24, and 48 [For

Week 48, BDQ and M2 only]). Subjects will be excluded from the PK analysis if their data did not allow for accurate assessment (eg, incomplete administration of the study drug; missing information of dosing and sampling times).

For descriptive statistics of the plasma BDQ, M2, CAM and 14-OH-CAM concentrations, following data handling rules will be applied:

- Data from samples outside Visit window rule and Time window rule specified in Table 2 and Table 6 will be excluded in the calculation.
- BQL will be substituted with “0 (zero)”.
- Number of plasma concentration data will be calculated based on the number of subjects with measurable value including BQL.
- When more than half (>50%) of plasma concentration are BQL at each scheduled time point, mean, median, and minimum will be shown as “BQL”, and SD, and %CV will be shown as “NC” (not-calculated), respectively. If all plasma concentrations are BQL, maximum will also be shown as “BQL”.
- When number of plasma concentration data is equal to or less than 2, only N and mean will be calculated and SD, %CV, median, minimum and maximum will be shown as “NC” regardless of the proportion of BQL, respectively.
- If the dose level is modified from the initially planned dose or prior to blood sampling day, plasma concentration data for that day will be excluded from the descriptive statistics.

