#### 5.7.1.2. Population Pharmacokinetic Analysis

Population PK (popPK) analysis of plasma concentration-time data of BDQ (and M2, if needed) will be performed with nonlinear mixed-effects modeling (NONMEM) approach. If deemed necessary, data will be combined with data from other studies. Details will be given in a population PK analysis plan and the result will be presented in a separate report.

In the popPK analysis, based on the individual plasma concentration-time data, using the actual dose taken and the actual sampling times, PK parameters ( $C_{max}$ ,  $C_{trough}$  [trough concentration],  $AUC\tau$ ) of BDQ at Day 1, Weeks 2, 8, 12, 24, and 48 will be derived. If deemed necessary, a similar analysis for  $C_{max}$ ,  $C_{trough}$ ,  $AUC\tau$  will be performed for M2.

Descriptive statistics (N, mean, standard deviation, %CV, median, minimum and maximum) will be calculated to summarize PK parameters of TMC207 (and M2, if needed) at Day 1, Weeks 2, 8, 12, 24, and 48.

For descriptive statistics of the PK parameters of BDQ (and M2, if needed) from population pharmacokinetics, following parameters will be reported.

- $C_{\max}$ ,  $C_{\text{trough}}$  and  $AUC_{\tau}$

The PK parameters of BDQ (and M2, if needed) will be tabulated and summarized at Day 1, Weeks 2, 8, 12, 24, and 48, respectively.

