### 5.7.1.3. Generating Pharmacokinetic Profiles

The following graphs will be produced by intervention group:

- Boxplots of the BDQ concentration at predose and 3 hours postdose (Day 1, Weeks 2, 8, 12, 24, and 48), respectively.
- Boxplots of the M2 concentration at predose and 3 hours postdose (Day 1, Weeks 2, 8, 12, 24, and 48), respectively.
- Boxplots of the CAM concentration at predose and 3 hours postdose (Day 1, Weeks 2, 8, 12 and 24), respectively.
- Boxplots of the 14-OH-CAM concentration at predose and 3 hours postdose (Day 1, Weeks 2, 8, 12 and 24), respectively.

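### The SAP summarises clarithromycin (CAM) concentrations across two planned doses, 400 mg bid in Japan and 500 mg bid in South Korea and Taiwan; a descriptive split by Region would let them be read by dose.

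*SAP*

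**What the plan says.** **Dose.** Protocol Table 2 sets different CAM doses by country. Footnote d reads "Daily dose of CAM on Day 1 is 800 mg (400 mg bid) in Japan and 1,000 mg (500 mg bid"; the second figure applies to South Korea and Taiwan. For adverse events the daily dose may be cut to 600 mg in Japan or 750 mg in the other two countries.

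**Endpoint.** SAP 1.1 lists PK exposure among the secondary endpoints, including "CAM (and metabolite 14-OH-CAM [optional]) at Day 1, Weeks 2, 8, 12, and 24".

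**Summaries.** SAP 5.7.1.1 plans descriptive statistics "to summarize plasma BDQ, M2, CAM and 14-OH-CAM concentrations at each sampling time point by intervention group and study day". The text after SAP Table 6 tabulates concentrations by intervention group and lists individual values. SAP 5.7.1.3 plans, again by intervention group, "Boxplots of the CAM concentration at predose and 3 hours postdose", with matching plots for 14-OH-CAM.

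**Dose rule.** SAP 5.7.1.1 also has an exclusion that begins "If the dose level is modified from the initially planned dose or prior to blood sampling day"; that day's concentrations are then left out of the descriptive statistics.

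**Modelling.** SAP 5.7.1.2 says "Population PK (popPK) analysis of plasma concentration-time data of BDQ (and M2, if needed) will be performed". Protocol 9.4.7 says that baseline characteristics "will be tested as potential covariates affecting PK parameters", in the same bedaquiline (BDQ) model. CAM is not modelled.

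**Region.** SAP Table 7 defines Region as Japan or non-Japan. SAP 5.3.4 applies subgroup analysis to the primary estimand only.

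**The concern.** A mean or median over participants on 800 mg/day and participants on 1,000 mg/day describes neither dose. It also shifts with the country mix, which is an accident of recruitment.

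The exclusion rule shows that the SAP already treats mixed doses as a problem in these tables, but it removes only unplanned differences. A Korean participant reduced to 750 mg/day is dropped, while a Japanese participant on the planned 800 mg/day is averaged with Koreans on 1,000 mg/day.

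What is at stake is whether a declared secondary endpoint can be interpreted. A reader who wants the CAM level at either planned dose would have to rebuild it from the listings.

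**Working it through.** There is no planned figure to reproduce here, because the point concerns grouping. The check has four steps.

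**1. Is there a split anywhere?** The planned CAM outputs are:
- the descriptive table (SAP 5.7.1.1): by group and study day;
- the tabulation after SAP Table 6: by group, plus individual listings;
- the boxplots (SAP 5.7.1.3): by group;
- the QTcF scatter plots and correlations (SAP 5.7.2): from each intervention group;
- the mean and median profiles (Protocol 9.4.7, where the metabolite is written 4-OH CAM): no grouping by dose or region stated.

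None is stated to be split by dose, country or region, and no dose normalisation is planned.

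**2. Does Region separate the doses?** Yes, for on-treatment samples. South Korea and Taiwan share 500 mg bid and Japan alone has 400 mg bid, so the existing two-level variable matches the two planned doses. Samples taken after a dose change are already excluded.

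**3. How far is the pooled mean from each dose level?** The dose ratio is 400/500 = 0.8. Two inputs are assumptions, because the documents do not give them: levels are dose-proportional, and Japan's share p is 50%, 70% or 90%.

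Pooled mean relative to the 500 mg bid level: m = 0.8p + (1 − p). Relative to the 400 mg bid level: m/0.8.

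| p | m | versus 500 mg bid | m/0.8 | versus 400 mg bid |
|---|---|---|---|---|
| 0.5 | 0.90 | −10% | 1.125 | +12.5% |
| 0.7 | 0.86 | −14% | 1.075 | +7.5% |
| 0.9 | 0.82 | −18% | 1.025 | +2.5% |

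Pooled coefficient of variation (CV), for an assumed within-dose CV of c:

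CV = √[p(0.8c)² + (1 − p)c² + p(1 − p)(0.2)²] / m

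| c | p = 0.5 | p = 0.7 | p = 0.9 |
|---|---|---|---|
| 30% | 32.2% | 32.0% | 31.0% |
| 40% | 41.8% | 41.6% | 40.8% |
| 60% | 61.4% | 61.3% | 60.6% |

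Pooling therefore moves the centre and leaves the spread almost unchanged.

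This arithmetic does not apply to Day 1 predose. Inclusion criterion 6.2 allows macrolide-containing treatment to be ongoing at entry, and Protocol 6.8 requires a washout of rifamycin only. Day 1 predose CAM reflects prior treatment, and a Region split does not turn it into single-dose cells.

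**4. How large would the new columns be?** With 62 planned per group, the non-Japan count is 62(1 − p):
- p = 0.5: 31;
- p = 0.7: 18.6, about 19;
- p = 0.9: 6.2, about 6.

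With 6 participants and a CV of 40%, the standard error of the mean is 40%/√6, about 16%.

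**The case against.** The best case against is that this is a matter of preference. The tables are descriptive and individual concentrations are listed. Randomisation is stratified by country (Protocol 6.3), so both arms should have a similar dose mix. The split would also say least where pooling misleads most: at a 90% Japanese share the pooled mean is 18% below the 500 mg bid level, but the non-Japan column then has about 6 participants per group. Region is not a clean dose contrast either. Table 2 also varies ethambutol dosing by country, and for rifabutin it says "The dose of RBT is based on the recommended dose in each country". In Group B the rule for choosing rifampicin or rifabutin differs as well.

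All of this stands. It limits the point to a labelled descriptive addition and is the reason to keep the pooled tables. It does not make the pooled figure interpretable by dose.

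A reader might infer three stronger things that the documents do not support:

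- **That the pooled tables and boxplots are the only CAM summaries.** They are not. Protocol 9.4.7 adds mean and median profiles, and relationships of CAM PK to safety and outcome are also planned. The gap is that none of these is stated to be split.
- **That the comparison of CAM levels between arms is biased.** Stratification by country argues against any systematic bias.
- **That BDQ and M2 need the same split, or that the BDQ dose is poorly justified.** Protocol 4.3 did simulate BDQ with CAM 500 mg bid, which is not the Japanese dose. But BDQ dosing is the same in all three countries, and the documents do not say how BDQ exposure differs between CAM 400 and 500 mg bid; the difference may be nil. The population PK plan is a separate document, not available here, and may already examine covariates.

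**Conclusion.** The point holds for CAM and 14-OH-CAM: their planned summaries mix two planned doses, and a variable that separates those doses already exists in the SAP. The distances of 10–18% and 2.5–12.5% rest on assumed dose proportionality and an assumed Japanese share. They would shrink towards zero if CAM levels depended little on dose over this range. The primary test and the futility decision do not use these tables. This is an optional, low-severity improvement in how a secondary endpoint is reported.

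**What to change.** In SAP 5.7.1.1 and 5.7.1.3, keep the pooled tables and boxplots. Add columns and boxplots by Region (Japan, non-Japan) for CAM and 14-OH-CAM in both intervention groups. Label them descriptive and add two notes: Day 1 predose values reflect treatment before the study, and Region also differs in ethambutol and rifabutin dosing, so the contrast does not isolate the CAM dose. No change is asked for in the BDQ, M2 or population PK outputs.

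The cost is a few lines of SAP wording and some extra table columns and plots, with no new data. The drawback is thin non-Japan cells if most participants are Japanese, so each column should show its N.

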- q. In case of recurrence (relapse/reinfection) or in case of acquired resistance (at least 4-fold increased MIC) to BDQ is indicated by DST result, baseline and postbaseline isolates will be identified using WGS or VNTR if necessary. If more than 1 postbaseline positive culture (isolate) showing resistant is available the last culture positive sample will be tested for VNTR and/or WGS in addition to the baseline culture positive sample.
- r. Lung function test on Day 1 will be acceptable within 1 week prior to Day 1.
- s. Chest CT scans taken within 6 months prior to screening are acceptable.
- t. Single sparse blood samples will be collected for measurement of plasma concentrations of BDQ (and M2 [optional]). These samples can be taken at any time after intake of BDQ on the day, but the date and time of the second to last and the last administration of BDQ and CAM, respectively, and the date and time of blood draw must be recorded.
- u. Two blood samples will be drawn: one just before intake of BDQ or first intake of CAM in the visit, and the second sample between 2 to 4 hours after the intake. The date and time of the last study drug administrations of BDQ and CAM, respectively, prior to the first PK samples and the date and time of the study drug administrations immediately after the first PK samples must be recorded. The date and time of the blood draw must be recorded.
- v. Extra visits will be required for participants meeting certain grading thresholds for changes in QTcF. All ECGs will be performed in triplicate (3 ECGs within 5 minutes) and must be of good quality (stable baseline, free of interference and artefact). The ECG machine dedicated for this study must be used. All tracings will be transmitted for blinded central analysis. ECG at 2-4 hours post-dose of BDQ and CAM will be obtained at Week 2, Week 12, Week 24 and Week 48. ECG at pre-dose of BDQ and CAM will be obtained at Day 1, Week 4, Week 6, Week 8, Week 16 and Week 32. Those ECG should be performed within 20 minutes prior to PK blood sampling at every time point whenever possible. ECG will be performed before blood sampling at the other visit where time points of ECG measurement are not specified.

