## 6.7. Treatment of Overdose

There is no experience with the treatment of acute overdose with BDQ.

For this study, any dose of BDQ greater than 400 mg within a 24-hour time period (-12 hour) from first day to 14 days after the first dose and 200 mg within a 72-hour time period (-24 hour) from 15 days will be considered an overdose. The sponsor does not recommend specific intervention for an overdose. Removal of unabsorbed BDQ may be achieved by gastric lavage or aided by the administration of activated charcoal. Since BDQ is highly protein-bound, dialysis is not likely to significantly remove BDQ from plasma.

Refer to the local package insert of the comparator rifamycin (RFP or RBT) for advice on treatment of overdose.

In the event of an overdose, the investigator or treating physician should:

- Contact the Medical Monitor immediately.
- Evaluate the participant to determine, in consultation with Medical Monitor, whether study intervention should be interrupted or dose should be reduced.
- Closely monitor the participant for AE/SAE and laboratory abnormalities. General measures to support basic vital functions including monitoring of vital signs and ECG (QT interval) should be taken in case of deliberate or accidental overdose.
- Obtain a plasma sample for PK analysis within 3 days from the date of the last dose of study intervention if requested by the Medical Monitor (determined on a case-by-case basis).
- Document the quantity of the excess dose as well as the duration of the overdosing in the eCRF.

Decisions regarding dose interruptions or modifications will be made by the investigator in consultation with the Medical Monitor based on the clinical evaluation of the participant.

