## 8. STUDY ASSESSMENTS AND PROCEDURES

### Overview

The Schedule of Activities (SoA) summarizes the frequency and timing of efficacy, PK, and safety measurements applicable to this study.

The following time windows are allowed:

- For visit Weeks 2, 4, 6, 8, 10, and 12 ( $\pm 2$  days)
- For visit Weeks 16, 20, and 24 ( $\pm 3$  days)
- For visit Weeks 28, 32, 36, 40, 44, 48, 52, 56, and 60 ( $\pm 4$  days)

In case of scheduling visit according to above time windows, the investigators should ensure that 4-week sputum collection interval does not fall below 25 days.

All PRO (SGRQ and QOL-B NTM module) assessments should be conducted/completed before any tests, procedures, or other consultations to prevent influencing participant perceptions. The questionnaires will be completed by the investigator after interviewing the participant and the data will be entered into the eCRF by the investigator/study-site personnel. Refer to the PRO completion guidelines for instructions on the administration of PROs.

If multiple assessments are scheduled for the same timepoint, it is recommended that procedures be performed in the following sequence: noninvasive procedures should be collected first before invasive procedure (questionnaire/interview/ECG, vital sign/physical examination/CT scan/audiology/visual examinations/fundoscopy, then sputum sample collection, and blood sampling). ECG and blood collections for PK assessments should be kept as close to the specified time as possible. Other measurements may be done earlier than specified timepoints if needed. Actual dates and times of assessments will be recorded in the source documentation and eCRF.

The total blood volume for the study is approximately 68 to 115.5 mL (52 mL [Group A] for pharmacokinetics and 20 mL [Group B], and 2 mL for pregnancy testing [women of childbearing potential only]).

The total blood volume to be collected from each participant will be approximately 68 to 115.5 mL.

For each participant, the maximum amount of blood drawn from each participant in this study will not exceed 115.5 mL.

Repeat or unscheduled samples may be taken for safety reasons or for technical issues with the samples.

If the unscheduled PK samples are taken, the date and the time of the blood draw must be recorded.

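### The Week 2 summary and boxplots of raw bedaquiline and M2 concentrations pool samples from both sides of the planned Day 15 step from 400 mg daily to 200 mg twice weekly

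*SAP*

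**What the plan says.** Protocol Table 2 gives the BDQ schedule as "Loading phase (Week 1-2): 400 mg qd, Maintenance phase (Week 3-48): 200 mg biw with at least 72 hours between doses". The overdose definition in protocol 6.7 also changes its limit at about this point; its higher limit applies "from first day to 14 days after the first dose".

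The Schedule of Activities puts the Week 2 visit on study day 15 ± 2. Protocol Section 8 repeats the two-day tolerance "For visit Weeks 2, 4, 6, 8, 10, and 12". Two PK samples are due at that visit: "one just before intake of BDQ or first intake of CAM in the visit", and a second 2 to 4 hours after intake (Schedule of Activities, footnote u).

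SAP 5.7.1.1 summarises BDQ, M2, clarithromycin (CAM) and 14-OH-CAM concentrations "at each sampling time point by intervention group and study day", with Week 2 as one of the listed days. SAP 5.7.1.3 adds boxplots for the same days. The sample screen is "Data from samples outside Visit window rule and Time window rule specified in Table 2 and Table 6 will be excluded in the calculation". Table 2 of the SAP gives Week 2 the window [2,22]. Table 6 accepts any predose sample taken before the visit dose and any postdose sample 96 to 288 minutes after it. A further rule drops a day's data when the dose has been modified from plan.

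For model-based exposure, SAP 5.7.1.2 says: "The PK parameters of BDQ (and M2, if needed) will be tabulated and summarized at Day 1, Weeks 2, 8, 12", continuing to Weeks 24 and 48. The AUC is labelled AUCtau at every visit. Protocol Table 1 uses AUC over 24 h at Week 2 and over 168 h at Weeks 24 and 48.

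**The concern.** A row labelled Week 2 will be read as one dosing condition. As specified it holds at least two: postdose values after 400 mg and postdose values after 200 mg. Even a participant seen exactly on Day 15 contributes a trough after the last 400 mg dose to the predose row and a value after 200 mg to the postdose row. The mean, %CV and boxplot then depend on how visits happened to fall within the five-day window. Part of the apparent between-participant variability would be scheduling, not pharmacokinetics.

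Protocol 8.4.1 asks for exposure in the loading and maintenance phases, and Week 2 is the natural place to look for the end of loading. Neither document says which phase the Week 2 raw-concentration row represents.

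**Working it through.** **1. The windows.** The Week 2 target is 2 × 7 + 1 = Day 15, as in SAP Table 2. Its upper bound is the midpoint to the Week 4 target, (15 + 29)/2 = Day 22; its lower bound is the day after baseline, Day 2. The Table 6 postdose limits are 0.8 × 120 = 96 min and 1.2 × 240 = 288 min. The stated figures reproduce.

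**2. What the screen removes.** Protocol-permitted days are 15 ± 2 = Days 13 to 17. All five lie in [2,22], so the window excludes none. The full window holds 13 loading days (2–14) and 8 maintenance days (15–22).

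**3. Planned dose by visit day.** Days 13–14: 400 mg. Days 15–17: after the step to 200 mg. The predose gap is 24 h on Days 13, 14 and 15. It becomes 48 h on Day 16 and 72 h on Day 17 if the first 200 mg dose is held until the visit.

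**4. The modified-dose rule.** The 200 mg dose is the planned dose, so the step is not a modification. Reading the rule to cover it would also remove Weeks 8, 12, 24 and 48, when everyone is on 200 mg.

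**5. Illustrative size for BDQ.** Assume one compartment, instantaneous absorption, 14 daily doses of 400 mg, and a first 200 mg dose at any visit from Day 15. With half-life h and r = 2^(−24/h), the predose amount after n daily doses is 400 × (r + r² + … + rⁿ), and it falls by a further factor r for each day without a dose. The postdose value is (predose + visit dose) × 2^(−3/h). The last factor cancels in ratios, so the postdose ratio to Day 14 is (predose + visit dose)/(Day 14 predose + 400).

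Half-lives: 24 h is the effective value in protocol 2.2. 38.1 h is 24/0.63, applying the 37% fall in clearance with CAM (protocol 4.3) at unchanged volume. 72 h is an assumed upper value.

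- h = 24, Day 15: (400 + 200)/(400 + 400) = 0.75.
- h = 24, Day 17: (100 + 200)/800 = 0.375.
- h = 72, Day 15: (1,478 + 200)/(1,463 + 400) = 0.90.
- h = 72, Day 17: (931 + 200)/1,863 = 0.61.

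Ratios to a Day 14 visit:

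| Visit day | Visit dose | Predose, h = 24 / 38.1 / 72 | Postdose, h = 24 / 38.1 / 72 |
|---|---|---|---|
| 14 | 400 mg | 1.00 / 1.00 / 1.00 | 1.00 / 1.00 / 1.00 |
| 15 | 200 mg | 1.00 / 1.00 / 1.01 | 0.75 / 0.82 / 0.90 |
| 16 | 200 mg | 0.50 / 0.65 / 0.80 | 0.50 / 0.59 / 0.74 |
| 17 | 200 mg | 0.25 / 0.42 / 0.64 | 0.38 / 0.45 / 0.61 |

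Postdose values are thus 10–25% lower on Day 15 and 39–62% lower on Day 17. No figure was worked out for M2.

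**The case against.** The strongest reply is that the listed endpoint is PK exposure. For BDQ this comes from a population model that uses each participant's actual doses and sampling times (protocol 8.4.3, SAP 5.7.1.2). A sample after 200 mg, or after a longer gap, is modelled as such. Protocol Table 1 also holds model-simulated ratios, so its counterpart is the model output and not the raw rows. This stands. A reader might infer that the secondary exposure endpoint is itself corrupted; the documents do not support that.

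Other stronger readings also fail:

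- *That the wide Day 2–22 window is the cause.* Narrowing it to Days 13–17 would still keep every permitted day and separate nothing.
- *That predose values are mixed throughout.* On Days 13–15 all are 24 h troughs after 400 mg.
- *That visits without a BDQ dose are certainly pooled.* If the first 200 mg dose was taken before the visit, the 72 h minimum can rule out a visit dose, and Table 6 may then drop the postdose sample. The documents do not say whether the visit dose in Table 6 could mean CAM intake, or whether the 72 h runs from the last loading dose.
- *That one missing time removes a whole participant.* The text is "Subjects will be excluded from the PK analysis if their data did not allow for accurate assessment", a judgement clause with examples. Elsewhere the same section excludes by sample and by day. No rate of participant loss can be derived from it.
- *That AUCtau is not comparable across visits.* The detail is assigned to a separate population PK analysis plan. The SAP can be asked to state the interval, not faulted for a wrong one.

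It may also be said that individual concentrations are listed and nothing here is tested. True, but a listing does not correct a summary row that combines two doses.

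**Conclusion.** The point holds for the Week 2 descriptive summary and boxplots of raw BDQ and M2 concentrations. The mixing of doses follows from the calendar and the stated rules and needs no pharmacokinetic assumption. Its size does: the ranges rest on a one-compartment simplification, half-lives of 24 to 72 h, and a first 200 mg dose taken at the visit. The protocol describes a multiphasic decline in animals and a terminal half-life of about 5.5 months in patients, so the true size is uncertain. It also depends on how many visits fall on each day, which is unknown.

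This is a cheap improvement to a descriptive secondary output. CAM and its metabolite are unaffected by the BDQ step.

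**What to change.** In SAP 5.7.1.1 and 5.7.1.3, for BDQ and M2 at Week 2 only, present predose and postdose concentrations in separate rows and boxplots by last dose taken (400 or 200 mg) and time since the previous dose. Use recorded dosing, not calendar day, because protocol Table 3 lets loading run past Day 14 after an interruption. Footnote u of the Schedule of Activities already requires the dose dates and times around these samples.

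In SAP 5.7.1.2, name the interval behind AUCtau: AUC over 24 h at Day 1 and Week 2, and over 168 h at the maintenance visits. This follows protocol Table 1 where it gives a value (Weeks 2, 24 and 48) and extends the same convention to Day 1 and Weeks 8 and 12.

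Optionally, state that a missing dose or sampling time excludes the affected sample, not the participant.

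The cost is SAP wording and programming. The downside is smaller numbers per Week 2 row, and the postdose row after 400 mg will come mainly from Day 13–14 visits. No change to dosing or to the visit schedule is involved.
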